### Determination of Subjects for Analysis

All subjects that completed 4 weeks of elevated night pacing. Subjects that were unable to tolerate or withdrew from the treatment during the first 4 weeks because of safety or other issues will not be included in this efficacy analysis. Subjects that did not take the 6 Minute Walk Test at either baseline or week 4 will be assigned a distance of 0 for the missed visit. A sensitivity analysis may be done excluding subjects instead of assigning a distance of 0.

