## 9.4. Exclusion Criteria

Subjects must not meet any of the following exclusion criteria to be eligible to participate in the study:

EXC 1: Subject has permanent AF or AF noted on baseline interrogation rhythm strip

EXC 2: Subject has uncontrolled BP; (systolic pressure needs to be  $>$ 100mmHg and  $<$ 160mmHg on medications)

EXC 3: Subject has severe stenosis of the aortic or mitral valve, defined as a valve area less than or equal to 1.0 cm^2 or subject has severe regurgitation of the aortic or mitral valve.

EXC 4: Subject has symptomatic COPD requiring oxygen

EXC 5: Subject's Pacemaker has less than 6 months of Pacemaker battery life

EXC 6: Subject had an aortic valve replacement (surgical or TAVR) procedure less than 9 months prior to enrollment.

EXC 7: Subject's programmed upper rate limit is less than 100 bpm because of concerns of elevated pacing

EXC 8: Subject is unable or unwilling to perform the 6 Minute Walk Test at all scheduled study visits

EXC 9: Subject is currently enrolled or planning to enroll in a potentially confounding trial during the course of the study (co-enrollment in concurrent studies is only allowed when documented pre-approval is obtained from the Medtronic study manager)

EXC 10: Subject is pregnant

EXC 11: Subject meets any exclusion criteria required by local law

EXC 12: Subject's life expectancy is less than 12 weeks

EXC 13: Subject with medical condition that precludes the patient from participation in the opinion of the investigator

EXC 14: Subject has known coronary disease with Class II angina

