#### 7.1.2. Clinical Investigation Plan (CIP) Deviations

A study deviation is defined as an event within a study that did not occur according to the Clinical Investigation Plan or the Clinical Trial Agreement.

Prior approval by Medtronic is expected in situations where the investigator anticipates, contemplates, or makes a conscious decision to deviate. Prior approval is not required when a deviation is necessary to protect the safety, rights or well-being of a subject in an emergency or in unforeseen situations beyond the investigator's control (e.g. subject failure to attend scheduled follow-up visits, inadvertent loss of data due to computer malfunction, inability to perform required procedures due to subject illness, blood sample or echo lost at Core Lab).

For medically justifiable conditions which preempt a subject's ability to complete a study-required procedure, it may be permitted to report only one deviation which will apply to all visits going forward. This may also apply for other unforeseen situations (e.g. the subject permanently refuses to complete a study required procedure and the data will not contribute to the primary endpoint analysis). However, prior approval from Medtronic is required for such situations.

All study deviations must be reported to Medtronic regardless of whether they are medically justifiable, pre-approved by Medtronic, an inadvertent occurrence, or taken to protect the subject in an emergency. The deviation must be recorded in Oracle Clinical. Refer to the CIP for an explanation for the deviations.

In the event the deviation involves a failure to obtain a subject's informed consent, or is made to protect the life or physical well-being of a subject in an emergency, the deviation must be reported to the IRB as well as Medtronic as soon as possible but no later than five (5) working days, or according to local requirements. Reporting of all other study deviations should comply with the IRB policies and/or local laws and deviations must be reported to Medtronic as soon as possible upon the site becoming aware of the deviation.

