### Analysis Methods

A paired comparison of the value at the end of the period compared to the value at the start of the period will be calculated. A one-sided paired t-test will be performed testing the hypothesis

$$H_0: \mu \leq 0$$

$$H_a: \mu > 0$$

Where  $\mu$  = difference in 6 Minute Walk Test distance from baseline to week 4 visit

SAS code similar to the following will be used to evaluate the 4 week 6 Minute Walk Test endpoint:

```
PROC TTEST;
  PAIRED sixminwalk0*sixminwalk4;
RUN;
```

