### Analysis Methods

A paired comparison of the scores at the 8 week visit compared to the score at the 4 week visit period compared to the value at the start of the period will be calculated. A one-sided paired t-test will be performed testing the hypothesis

$$H_0: \mu_{ON} \leq \mu_{OFF}$$

$$H_a: \mu_{ON} > \mu_{OFF}$$

Where  $\mu_{ON}$  = difference in 6 Minute Hall Walk distance from week 4 to week 8 in subjects randomized to the ON arm and  $\mu_{OFF}$  = difference in 6 Minute Hall Walk distance from week 4 to week 8 in subjects randomized to the OFF arm.

SAS code similar to the following will be used to evaluate the effect of the study therapy on the 6 Minute Hall Walk endpoint between week 4 and week 8:

```
PROC TTEST;
  CLASS trt;
  VAR sixminwalkdiff;
RUN;
```

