### Determination of Subjects for Analysis

All subjects that completed 4 weeks of elevated night pacing. 6 Minute Walk Test distance at time of exit will be used for subjects that do not complete the full 4 weeks of participation in the study from week 4 to week 8. Subjects that did not take the 6 Minute Walk Test at either week 4 or 8 will be assigned a distance of 0 for the missed visit. A sensitivity analysis may be done excluding subjects instead of assigning a distance of 0.

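### SAP 7.9.5 scores a missed start-of-period 6 Minute Walk as 0 m, so that subject's whole end-of-period walk is analysed as improvement

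*SAP*

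**What the plan says.** For the 4-week walk endpoint, SAP 7.9.5 (Determination of Subjects for Analysis) states: "Subjects that did not take the 6 Minute Walk Test at either baseline or week 4 will be assigned a distance of 0". For the 8-week endpoint it states: "Subjects that did not take the 6 Minute Walk Test at either week 4 or 8 will be assigned a distance of 0". In both places the zero attaches to whichever visit was missed.

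The quantities analysed are the "difference in 6 Minute Walk Test distance from baseline to week 4 visit" and, between arms, the "difference in 6 Minute Hall Walk distance from week 4 to week 8 in subjects randomized to the ON arm" against the same difference in OFF. A positive value means improvement, and both tests are one-sided.

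The only alternative offered is optional: "A sensitivity analysis may be done excluding subjects instead of assigning a distance of 0". SAP 7.4 rules out imputation unless an analysis section specifies it, so this explicit rule governs. Protocol 14.1.5 has no zero rule for this endpoint, and SAP 7.10 does not list one among its corrections.

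For the 8-week endpoint the SAP also says "6 Minute Walk Test distance at time of exit will be used for subjects that do not complete the full 4 weeks" between weeks 4 and 8.

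**The concern.** Scoring a missed walk as 0 m can be defended as a worst case when the missed walk ends the period. At the start of the period the same zero is a best case for that subject's change. The rule does not separate the two, and it does not ask why the walk was missed.

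The rest of SAP 7.9 treats incomplete pairs differently. The MNLWHF and EQ-5D-5L analyses need adequate responses at both visits, and subjects without 4-week safety measurements are excluded by default.

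Protocol 5.1 names exercise capacity as what the therapy aims to improve. In a feasibility study the estimate itself is the main product. Under SAP 4.2 and 7.9.8, nominal significance at week 4 or week 8 also decides which effects are followed to later visits.

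**Working it through.** There is no plan figure to reproduce. Neither document gives a walk distance, SD, effect size or missing rate for this endpoint.

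**Inputs from the documents.** 30 treated subjects and 2:1 allocation (SAP 5.1), hence 20 ON and 10 OFF if all 30 are randomised; change scores and one-sided tests (SAP 7.9.5).

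**Assumptions.** End-of-period walk D = 200/300/400 m; SD of change 30, 50 or 80 m; one-sided 5%; one missed start walk; between-subject SD of distance 90 m in the simulations. The 8-week comparison is a two-sample t-test, as the SAP's code has it.

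**One subject, D = 300 m.**
- Baseline missed, 300 m at week 4: change = 300 − 0 = +300 m.
- Week 4 missed, 300 m at baseline and at week 8: 0 − 300 = −300 m at 4 weeks, then 300 − 0 = +300 m at 8 weeks.
- Both walks of a period missed: 0 − 0 = 0.

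**4 weeks, n = 30.** With no true change, one missed baseline shifts the mean by D/30:
- 200/30 = 6.7 m, 300/30 = 10.0 m, 400/30 = 13.3 m.
- Simulated type I error is 7–9% at SD 50–80 and 3–7% at SD 30. It can fall below 5% because the outlier also inflates the SD. Excluding the subject restores about 5%, if the miss is unrelated to the change.

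**8 weeks, shift in ON minus OFF.**

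| Missed week 4 walk in | Formula | D = 200 | D = 300 | D = 400 |
|---|---|---|---|---|
| ON | +D/20 | +10 m | +15 m | +20 m |
| OFF | −D/10 | −20 m | −30 m | −40 m |

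Device programming comes after the other visit procedures (Protocol 10.5), so the week 4 walk is taken while every subject is still paced at night. Whether it is missed cannot depend on the therapy received in weeks 4–8. If the miss falls on a random one of the 30 subjects, the expected shift is (20/30)(D/20) − (10/30)(D/10) = D/30 − D/30 = 0.

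**8 weeks, pooled power for a true +30 m at SD 50.**

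| Situation | D = 200 | D = 300 | D = 400 |
|---|---|---|---|
| No missed walk | 44% | 44% | 44% |
| Zero rule, miss in OFF (one chance in three) | 10% | 3% | under 1% |
| Zero rule, averaged over randomisation | about 34% | about 29% | about 23% |
| Affected OFF subject excluded | 42% | 42% | 42% |

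The average weights the two arms by 20/30 and 10/30. Solving for a miss in ON gives (0.34 − 0.10/3) × 1.5 = 46%, (0.29 − 0.03/3) × 1.5 = 42% and (0.23 − 0.005/3) × 1.5 = 34%. So even a miss that moves the estimate towards ON adds little or no power, because the outlier widens the SD. At SD 80 average power falls from 24% to roughly 17–22%.

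**The case against.** **Missed baseline walks should be rare.** This stands. Protocol 9.4 EXC 8 excludes anyone for whom "Subject is unable or unwilling to perform the 6 Minute Walk Test at all scheduled study visits". Protocol 10.9 requires the baseline walk and places programming after it, and Protocol 10.5 prefers a late visit to a missed one. The 4-week distortion needs a subject programmed without a required procedure. That limits how often it occurs, not its effect when it does. SAP 7.1.2 lists "inability to perform required procedures due to subject illness" among foreseen deviations, without giving a rate.

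**The 8-week comparison is randomised.** This also stands. A reader might infer that the rule systematically favours one arm, or that the expected power is the 10/3/under 1% of the OFF case. Neither follows: the bias averages about zero, and those figures describe one case in three.

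**False positives.** A reader might infer serious inflation of type I error. With one missed start walk the 4-week rate is 3–9%. At 8 weeks, with the miss in a random subject, it is about 0.5–4.7% pooled and 3.5–6.1% with unequal variances. The case rests on the realised estimate and on precision.

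**Zero may be true.** If a subject really could not walk at week 4, later recovery is real change. That is fair for such a subject, but the rule covers any untaken test, whatever the reason.

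**Exit distance versus 0.** A reader might see a contradiction for subjects who exit between weeks 4 and 8, since no order is stated and the schedule shows no walk at early exit. The text can be read with the specific exit rule first, and a follow-up form may be completed at exit where applicable. It concerns end-of-period values only, so stating the order is a clarification.

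**Little rests on this endpoint.** It is ancillary, unpowered and unadjusted, and the decision to proceed is tied to 4-week safety and tolerability (SAP 6). This bears on severity, not on whether the rule is right.

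**Conclusion.** The concern holds in limited form. As written, SAP 7.9.5 gives a wrong value for any subject whose start-of-period walk is missing and whose end-of-period walk was taken: the whole end walk is scored as gain.

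Per missed start walk, under the assumed distances, the single-arm 4-week mean is biased upwards by 7–13 m, in a situation that should be rare. The 8-week difference moves by 10–20 m towards ON or 20–40 m against it, depending on the arm. That averages to about zero but costs roughly 10 to 21 points of pooled power at SD 50 (44 − 34 and 44 − 23). The mean shifts are exact arithmetic given D. The power figures depend on the assumed SD and a true +30 m, neither of which the documents supply.

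Severity is minor to moderate. Scoring a missed end-of-period walk as 0 is not in question here.

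**What to change.** In SAP 7.9.5:
- **4-week endpoint:** state that a missed baseline walk is not imputed and that the subject is excluded from this analysis.
- **8-week endpoint:** state the same for a missed week 4 walk.
- **Both:** change the sensitivity analysis from one that may be done to one that will be done, restricted to subjects with both walks of the period.

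How to treat a missed end-of-period walk remains the sponsor's choice. As an optional clarification, say that a distance measured at exit takes precedence over 0.

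The cost is wording in two places and one analysis that becomes mandatory; no new data are needed. Excluding one OFF subject at 8 weeks costs at most about 3 points of pooled power for a true +30 m: 81% to 78% at SD 30, 44% to 42% at SD 50 and 24% to 23% at SD 80. A missed week 4 walk could still be 0 as the 4-week end value while being treated as missing at 8 weeks. That asymmetry is deliberate and should be stated.

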## 6 Minute Walk Test Distance – 8 weeks

### Hypothesis

There is an improvement in the 6 Minute Walk Test distance from an additional 4 week period of elevated night pacing after an initial 4 week period of elevated night pacing

compared to that period of 4 weeks with the elevated night pacing programmed OFF after the initial 4 weeks period of elevated night pacing.

### Analysis Methods

A paired comparison of the scores at the 8 week visit compared to the score at the 4 week visit period compared to the value at the start of the period will be calculated. A one-sided paired t-test will be performed testing the hypothesis

$$H_0: \mu_{ON} \leq \mu_{OFF}$$

$$H_a: \mu_{ON} > \mu_{OFF}$$

Where  $\mu_{ON}$  = difference in 6 Minute Hall Walk distance from week 4 to week 8 in subjects randomized to the ON arm and  $\mu_{OFF}$  = difference in 6 Minute Hall Walk distance from week 4 to week 8 in subjects randomized to the OFF arm.

SAS code similar to the following will be used to evaluate the effect of the study therapy on the 6 Minute Hall Walk endpoint between week 4 and week 8:

```
PROC TTEST;
  CLASS trt;
  VAR sixminwalkdiff;
RUN;
```

### Determination of Subjects for Analysis

All subjects that completed 4 weeks of elevated night pacing. 6 Minute Walk Test distance at time of exit will be used for subjects that do not complete the full 4 weeks of participation in the study from week 4 to week 8. Subjects that did not take the 6 Minute Walk Test at either week 4 or 8 will be assigned a distance of 0 for the missed visit. A sensitivity analysis may be done excluding subjects instead of assigning a distance of 0.

### **Device-measured activity levels – 4 weeks**

#### Hypothesis

There is an improvement in daytime activity levels from baseline over a 4 week period of elevated night pacing.

## Analysis Methods

Activity levels over time will be characterized over time from baseline to the 4 week visit. Daily activity level is recorded by the Cardiac Compass feature in most devices. Since subjects enrolled in the study have had their pacemaker for at least 6 month, they will have activity levels prior to enrollment in the study. The daily activity levels in the 2 weeks prior to the date of therapy initiation (period 1) will be compared to daily activity levels around the 4 week visit. Specifically, the activity level on the date of the 4 week visit and the 3 days prior to and subsequent to that date will comprise the week 4 comparison group (period 2). Those periods will be retrieved from the Cardiac Compass activity level data using SAS code similar to the following, where the Activity\_Baseline data set contains all of the Cardiac Compass dates (entryday), along with the date of therapy initiation (therapydt) on each record.

```
DATA Activity_Week4;
  SET Activity_Baseline;
  IF -8 < entryday-therapydt < 0 THEN DO;
    period = 1;
    OUTPUT;
  END;
  IF -15 < entryday- therapydt LE -8 THEN DO;
    period=1;
    OUTPUT;
  END;
  /*      Straddle the week 4 date - the 4 week date and the 3 days
before and after the 4 week date */
  IF (w4date-3) LE entryday- therapydt LE (w4date+3) THEN DO;
    period=2;
    OUTPUT;
  END;
RUN;
```

The analysis will be performed using linear mixed effects modeling, using SAS code similar to

```
PROC MIXED DATA=Activity_Week;
  CLASS pt period;
  MODEL activityperday = period;
  RANDOM pt;
  LSMEANS period / PDIFF=all alpha=0.05;
RUN;
```

Additional analyses, using similar methodology, may be done to explore other potential effects of therapy, including whether there is an immediate impact on activity following therapy initiation.

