#### **10.5. Schedule of Events**

Clinical data is collected at designated time points throughout the study as indicated in Table 4 below. Data will be collected using eCRFs, an electronic data management system for clinical studies. See Section 16.2. Data Management for more information. At the baseline, 4 week, 8 week, and 12 week visits subjects are to fill out the MN Living with Heart Failure Questionnaire and perform a 6 Minute Walk Test. At the same visits, an echocardiogram must be done, for which instructions are provided in an Echocardiography Handbook (provided under separate cover). A blood draw must also be done,

(instructions are provided under separate cover.) The device programming should occur after all other study procedures are complete, except for the final device interrogation and save-to-media. The EQ-5D-5L Questionnaire will only be collected at the Baseline and 8 week visits.

In addition to eCRF data, non-eCRF data will be collected to include device interrogation files/save-to-media and digital echo data.

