### **10.9.1. Programming Recommendations at Baseline**

Table 6 lists the programming recommendations applicable to all study subjects. At the Baseline visit, when the Sleep Function is turned ON, the pacing rate will remain at the 100 bpm setting until 5:00 am the next day. Use of AAI (R) programming is not recommended due to the possibility of AV block occurring at higher rate pacing.

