## 5.3. Study Procedures

Clinical data is collected at designated time points throughout the study as indicated in Table 1 below. Data will be collected using eCRFs, an electronic data management system for clinical studies. At the baseline, 4 week, 8 week, and 12 week visits subjects are to fill out the MN Living with Heart Failure Questionnaire and perform a 6 Minute Walk Test. At the same visits, an echocardiogram must be done, for which instructions are provided in an Echocardiography Handbook (provided under separate cover). A blood draw must also be done, (instructions are provided under separate cover.) The device programming should occur after all other study procedures are complete, except for the final device interrogation and save-to-media. The EQ-5D-5L Questionnaire will only be collected at the Baseline and 8 week visits.

In addition to eCRF data, non-eCRF data will be collected to include device interrogation files/save-to-media and digital echo data.

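### The 4 week activity comparison has a study visit day in its after window but none in its before window, so a visit-day departure d shifts the result by d/7 in a direction the documents do not settle

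*SAP*

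**What the plan says.** **Before window.** SAP 7.9.5 (Device-measured activity levels, 4 weeks) takes the two weeks before therapy initiation as period 1. The code selects these days with two conditions: "IF -8 < entryday-therapydt < 0 THEN DO" and "IF -15 < entryday- therapydt LE -8 THEN DO".

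**After window.** Period 2 is "Specifically, the activity level on the date of the 4 week visit and the 3 days prior to and subsequent to that date". The code agrees: "IF (w4date-3) LE entryday- therapydt LE (w4date+3) THEN DO".

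**When therapy starts.** Protocol 10.9.1 describes pacing behaviour "At the Baseline visit, when the Sleep Function is turned ON", so therapy initiation is the Baseline visit day.

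**What happens on visit days.** SAP 5.3 says that at the Baseline, 4, 8 and 12 week visits "subjects are to fill out the MN Living with Heart Failure Questionnaire and perform a 6 Minute Walk Test". An echo and a blood draw are required at the same visits.

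**Model.** Daily activity is regressed on period with a random subject intercept. There is no visit-day term, and no sensitivity analysis drops the visit day. The hypothesis is an improvement in daytime activity from baseline.

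**Randomization.** Subjects are randomized 2:1 to ON or OFF at the 4 week visit (Protocol 10.11), and the OFF group is reprogrammed then (Protocol 10.11.2, Table 7).

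**The concern.** The two windows treat study visit days differently. A day that the study itself makes unusual is counted after therapy starts but not before. Protocol section 14 describes the first 4 weeks as single-arm and unblinded, so no control group removes the difference.

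The 8 week activity test is not exposed in the same way. Both of its windows contain a visit day, and it tests a period-by-treatment interaction between randomized arms.

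The after window also runs three days past randomization. For the OFF group those days follow withdrawal of the therapy whose effect the test is meant to describe.

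What is at stake is a nominal finding. Under SAP 7.9.8 a measurement significant at week 4 leads to follow-on tests of sustained effect, and SAP 7.5 plans no multiplicity adjustment.

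**Working it through.** **1. Days selected by the code.** Here w4date is read as days since therapy initiation, an assumption that the code's subtraction requires.

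- Period 1: the nearer-week condition gives days -7 to -1 and the farther-week condition gives days -14 to -8. Together they make 14 days. The strict upper limit drops day 0, the Baseline visit.
- Period 2: for a visit on day 28, days 25 to 31. That is 7 days, of which the visit day is one.

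Text and code agree on both windows.

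**2. Shift with no therapy effect.** Let d be the departure of visit-day activity from the subject's usual level. The model's period contrast is the period 2 mean minus the period 1 mean, so

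shift = d × 1/7 - 0 = d/7 ≈ 0.143d.

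The only study-imposed activity that the documents quantify is the 6-minute walk. If activity is recorded in minutes (assumption; the SAP names only a daily activity variable), the walk contributes at most 6/7 = 0.86 min/day.

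**3. Possible offset before therapy.** Enrollment may be a stand-alone visit (Protocol 10.8) up to 30 days before Baseline (Protocol 10.9), so it may fall in days -14 to -1. If every subject had one there with the same d, the shift would be d/7 - d/14 = d/14. Protocol Table 4 schedules no walk test at Enrollment.

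**4. What the shift does to the test.** Let s be the within-subject day-to-day SD. The documents give neither s nor d, so d is expressed in units of s. Under the SAP's random-intercept model, with days independent given the subject,

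SE = s × √[(1/14 + 1/7)/n].

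For n = 30, the top of the planned range, SE = s × √(0.2143/30) = 0.0845s. The table gives rejection rates from the noncentral t distribution, two-sided 5%, with no therapy effect. The SAP sets alpha at 0.05 without stating sidedness.

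| d (assumed) | Shift | n = 30, two-sided | n = 30, in the improvement direction | n = 20, two-sided |
|---|---|---|---|---|
| -0.5s | -0.071s | 13.5% | 0.3% | 10.6% |
| 0 | 0 | 5.0% | 2.5% | 5.0% |
| 0.25s | 0.036s | 7.1% | 6.2% | 6.4% |
| 0.5s | 0.071s | 13.5% | 13.2% | 10.6% |
| 1s | 0.143s | 39% | 39% | 28% |

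Simulation with 5,000 trials per setting at n = 30 gave two-sided rates of 4.5%, 7.3%, 13.3% and 38.1% for d = 0, 0.25s, 0.5s and 1s. With an offsetting enrollment visit in every subject, the simulated rates were about 6.5% at d = 0.5s and 12% at d = 1s. With the visit day dropped, the rate was 5.1% and the mean shift was close to zero, even with d = 1s.

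**5. Days after randomization.** Three of the seven days in period 2 follow the visit. Under 2:1 allocation one third of subjects are assigned to OFF, so about 1/3 × 3/7 = 1/7 of the period 2 subject-days follow assignment to OFF. If an activity effect ended at once on withdrawal (assumption), the estimate would be diluted by about 14%. If it faded slowly, the dilution would be smaller.

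**The case against.** A reader might infer that the asymmetry works in favour of the therapy, or that it produces large false-positive rates. The documents do not support either reading.

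- **Direction.** An upward bias needs a visit day to be more active than usual. The visit also includes an echo, a blood draw, a questionnaire, a physical assessment and two device interrogations, much of it likely to be sedentary. A less active day would hide a gain.
- **Size.** Large rates appear only when a large visit-day excess is assumed. The walk alone is worth under 1 min/day. The sample may also be below 30: the SAP says that most devices, not all, record daily activity, and it restricts the analysis to subjects who completed 4 weeks.
- **Day 0.** Its omission is sound. Therapy starts that day, and pacing stays at 100 bpm until the next morning. The issue is only that the 4 week visit day is not handled in the same way.
- **Weight.** The endpoint is ancillary in an unpowered study, the protocol promises only to characterize activity, the code is labelled as indicative, additional analyses are allowed, and the tests in SAP 7.9.8 are themselves exploratory.

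All of this stands, and it sets the severity. It does not remove the asymmetry. The windows are explicit in text and code, nothing in the model absorbs a visit-day departure, and an enrollment visit is optional and carries no walk test, so the offset is partial at best.

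**Conclusion.** The point holds as a minor one. Period 2 contains a study visit day as one of seven days and period 1 contains no Baseline visit day, so the single-arm 4 week contrast carries a shift of d/7. That follows from the SAP's own definitions.

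The sign and size of d are unknown. The only figure based on the documents is a ceiling of about 0.86 min/day from the walk, and it assumes that activity is counted in minutes. The rejection rates above are conditional on assumed values of d/s and should not be read as the expected error rate. A stand-alone enrollment visit could reduce the shift, to d/14 if every subject had one with the same departure.

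Separately, about one seventh of the period 2 subject-days follow assignment to OFF. This does not depend on d.

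No decision rule rests on this p-value. The change is worth making because it costs very little and nominal significance here leads to further tests.

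**What to change.** In SAP 7.9.5 (4 weeks), exclude the 4 week visit day and the days after it from period 2. One way is to use the 7 days ending the day before the visit, days -7 to -1 relative to it. In the code the condition becomes `(w4date-7) LE entryday-therapydt LE (w4date-1)`. Change the text and the code together.

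This keeps 7 days against 14, so under the SAP's model the standard error is unchanged and weekdays stay balanced. All period 2 days then precede randomization. A 14-day window before the visit would also remove the visit day, but it would move the measurement to about weeks 2 to 4, which is more than the problem needs.

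The 8 week activity analysis uses the same week 4 window as its period 1. State whether that window stays as written or follows the new definition, so that two meanings of week 4 activity do not coexist unexplained. A visit-day departure common to both arms cancels in that analysis either way.

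Cost: an edit to the SAP and no new data. The downside is that the window is centred about 4 days earlier than now.
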